### **6.4. Interim analysis**

An interim analysis will take place after the completion of recruitment of each age stratum. Data will be cleaned and locked before each interim analysis. The data will include any results until day 30.

### **6.5. Other aspects**

#### ***6.5.1. Subgroup analyses***

Since this is a stratified randomized trial, all analyses will be done by age-group.

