4.3 Sample size

The sample size for the phase 2 trial is based on non-inferiority of the BE-PEP regimen compared to the SDR-PEP regimen in terms of adverse events, in particular QTc prolongation. We assume that in the SDR group the mean QTc will be equal to that of a reference population, i.e. 384 ms (SD 20 ms) based on the Fridericia correction method. [29]

The sample size calculations were performed by simulation, in a scenario where there is truly no difference between the standard and experimental treatment. A sample size of 64 patients are required per arm to achieve 80% power in the comparison that the upper limit of a one-sided 95% confidence interval will be below the non-inferiority limit of +10 ms.

For this part of the trial we have selected a village with a total recorded population of 908, 51% of whom are aged 18 years or above. As explained in chapter 4.2 above, as a matter of precaution we will first enroll adults and preliminarily assess their outcomes before we will start enrolling minors. The numbers of adults to be enrolled will be proportional to the observed age distribution at the time of the 2022 survey. To arrive at an accurate estimate of mean QTc for adults as well as for minors, we will recruit 150 participants per study arm, approximately 75 adults and 75 minors.

Overall, all ages combined, our intended sample size of 150 in each arm, which will provide 99% power to show that the upper limit of a one-sided 95% confidence interval will be below the non-inferiority limit of +10ms, assuming that in the larger population QTc does not differ between those receiving SDR-PEP and those receiving BE-PEP. Sample size calculations were done in R version 4.0.2.[30]

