## **6. Statistical Methods**

### **6.1. Primary safety analysis**

The main objective about the difference in QTc between the two arms 24 hours after treatment administration will be assessed by calculating the 95% confidence interval for the difference.

Non-inferiority is established if the upper limit of a one-sided 95% confidence interval around the difference in means QTc 24 hours after treatment administration (BE-PEP - SDR-PEP) is below the non-inferiority limit of +10 ms.

Analysis of covariance (ANCOVA) or an equivalent regression model correcting for the baseline values of QTc will also be used to assess the primary objective. Alternatively, the individual difference scores will be calculated by subtracting the QTc values at baseline from the ones at day 1. The difference scores will be compared using a two-sample t-test.

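### The SAP sends all analyses to age-group level without saying that one all-ages, stratum-adjusted comparison decides the +10 ms QTc rule, the only comparison that the phase 2 sample size was powered for

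*SAP*

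**What the plan says.** SAP 6.1 defines one decision rule for the primary outcome: "Non-inferiority is established if the upper limit of a one-sided 95% confidence interval around the difference in means QTc 24 hours after treatment administration" (BE-PEP minus SDR-PEP) is below +10 ms. It adds an ANCOVA, or equivalent regression, correcting for baseline QTc. Age stratum appears in neither.

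SAP 6.5.1, in full, reads: "Since this is a stratified randomized trial, all analyses will be done by age-group". It makes no exception for the primary analysis. SAP 2.1 gives the strata as 18 years and above, 13-17 and 5-12, filled in proportion to the village population. SAP 6.5.2 foresees no multiplicity adjustment, and SAP 6.4 places an interim analysis after each stratum.

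Protocol 4.3 sizes the rule for the pooled sample: "Overall, all ages combined, our intended sample size of 150 in each arm, which will provide 99% power". It plans about 75 adults and 75 minors per arm so that mean QTc can be estimated accurately in each of those two groups. It gives no power for either group and no numbers for 13-17 and 5-12 separately.

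**The concern.** Stratified randomization is a reason to make one comparison that accounts for the strata. It is not a reason to repeat the whole analysis inside each stratum. The SAP draws the second conclusion and omits the first: 6.5.1 sends everything to age-group level, while the pooled comparison in 6.1 has no stratum term.

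Taken literally, the analysis report could carry a separate non-inferiority statement for each age group. In a stratum with a few dozen participants per arm, or fewer, the upper confidence limit lies 8 to 11 ms above the estimate, so an estimate near zero can miss a 10 ms margin purely because the group is small. Since the SAP does not say which result decides, a reader could also choose between the pooled and the stratum results after seeing them. The stake is a clear statistical report for the DSMB, which advises on phase 3.

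**Working it through.** **Inputs**
- Margin +10 ms, upper limit of a one-sided 95% interval (SAP 6.1).
- SD: "384 ms (SD 20 ms) based on the Fridericia correction method" (Protocol 4.3).
- True difference 0: "in a scenario where there is truly no difference between the standard and experimental treatment" (Protocol 4.3).
- 150 per arm, about 75 adults and 75 minors (Protocol 4.3), allocated 1:1 (SAP 2.1).
- Division of the minors between 13-17 and 5-12: not given. Assumed 37/38, 30/45, 25/50 and 20/55 per arm.

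**Formula.** With n per arm, the standard error of the difference is SE = SD × √(2/n). The rule is met if the estimate + t(0.95; 2n−2) × SE is below 10. Power is the noncentral-t probability of that event. As a check, the normal approximation is Φ(10/SE − 1.645).

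**The plan's own figure.** At n = 150, SE = 20 × √(2/150) = 2.31 ms and 10/2.31 = 4.33. Φ(4.33 − 1.645) = 99.6%, and noncentral t gives the same. The stated 99% is reproduced.

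The other stated figure is "A sample size of 64 patients are required per arm to achieve 80% power". At the one-sided 5% level, n = 2 × 20² × (1.645 + 0.842)²/10² = 49.5, so 50 per arm (51 with t). At one-sided 2.5% the same formula gives 62.8, so 63 (64 with t). The 64 therefore matches the upper end of a two-sided 95% interval. SAP 6.1 also describes the comparison as "assessed by calculating the 95% confidence interval for the difference" without giving the sidedness, so both levels are carried below.

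**Power within a stratum** (SD 20 ms, no true difference, one-sided 5%)

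| n per arm | SE (ms) | Upper limit above estimate (ms) | Power |
|---|---|---|---|
| 75 | 3.27 | 5.4 | 92% |
| 50 | 4.00 | 6.6 | 80% |
| 38 | 4.59 | 7.6 | 70% |
| 37 | 4.65 | 7.8 | 69% |
| 25 | 5.66 | 9.5 | 54% |
| 20 | 6.32 | 10.7 | 46% |

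At 20 per arm with the assumed SD, an observed difference of exactly zero would miss the margin.

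**At least one of three misses.** The strata are independent, so the chance is 1 minus the product of the three powers. For 75/37/38: 1 − 0.920 × 0.686 × 0.697 = 0.56. For 75/20/55: 1 − 0.920 × 0.463 × 0.832 = 0.65.

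| Split per arm (18+ / 13-17 / 5-12) | One-sided 5% | One-sided 2.5% | One-sided 5%, baseline correlation 0.6 |
|---|---|---|---|
| 75/37/38 | 56% | 72% | 29% |
| 75/30/45 | 58% | 73% | 31% |
| 75/25/50 | 60% | 75% | 36% |
| 75/20/55 | 65% | 79% | 43% |

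The last column replaces the SD by 20 × √(1 − 0.6²) = 16 ms. The correlation is an assumption; the documents give none. Simulation with 100,000 runs agreed for 75/37/38 (56% and 72%) and 75/25/50 (60% and 75%) in the two unadjusted columns.

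**Sensitivity.** At one-sided 5% without adjustment, the chance reaches 50% at an SD of about 19 ms (75/37/38) or 18 ms (75/25/50); below that it is under one half. For the same two splits, a baseline correlation of 0.5 gives 38-45% and 0.7 gives 17-24%. The pooled analysis misses in 1 − 0.996 = 0.4% of trials at one-sided 5%, or 0.9% at one-sided 2.5%.

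**The case against.** The best reply is that the sentence sits under a subgroup heading, that SAP 6.1 defines a single contrast between the arms, and that Protocol 4.3 ties the rule to all ages combined. Read together, the pooled comparison is the powered test and the age groups are subgroups. That is a sensible reading and probably the intended one. But the SAP does not state it, and the pooled comparison would still lack a stratum term.

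A reader might go further and infer that the trial is likely to fail non-inferiority, or that a missed stratum would signal QTc harm or stop enrolment of children. The documents do not support this. No passage requires every stratum to pass. Protocol 2.1.1 makes the phase 2 outcome the DSMB's advice, and Protocol section 8 leaves the clinical relevance of any QTc prolongation to its judgement. The steps to younger ages (Protocol 4.2 and 4.4) depend on QTc measurements and adverse events giving no concern, not on the +10 ms rule. The pause criteria contain no mean-difference rule.

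Two further points stand. The SAP also plans a baseline-adjusted analysis, under which a miss may be less likely than not. And age-specific summaries are part of a sequential design: when the adult stratum is complete there is no all-ages model to fit, so the interim looks cannot be replaced by one.

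**Conclusion.** The point holds as an unstated decision hierarchy and a missing stratum adjustment, and not as a rule that is bound to return a false failure. If the unadjusted 6.1 rule were applied in each of three strata with SD 20 ms and no true difference, at least one would miss in about 56-65% of trials. This rests on 75 adults and 75 minors per arm and on assumed divisions of the minors. With baseline adjustment at an assumed correlation of 0.6, it is about 29-43%. A miss would reflect a wide interval in a small group; the estimate would still be visible, and the pooled analysis keeps its 99% power. The case for change rests on clarity and on matching the analysis to the powered comparison, at almost no cost.

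**What to change.** In SAP 6.1 and 6.5.1, state that the final non-inferiority conclusion comes from one all-ages estimate adjusted for the three age strata, and also for baseline QTc in the ANCOVA already planned. Report the treatment difference in each age group, and in adults and all minors as the two groups that Protocol 4.3 recruited for, as estimates with confidence intervals and no separate pass/fail verdict. Keep the interim looks after each stratum as age-specific descriptive summaries.

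The cost is a few sentences of SAP wording and a stratum term in the model. Sample size, data collection and procedures do not change. The small downside is that no formal verdict is given for a single age group, which the sample size was not planned to provide.

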#### ***6.5.2. Multiplicity adjustment***

No adjustments for multiplicity are foreseen.

#### ***6.5.3. Missing data and sensitivity analysis***

Missing data will be reported, though all specified analyses are complete case analyses. If a significant proportion of missing values is observed, then imputation methodology will be considered in a sensitivity analysis, after communication with the research consortium.

#### ***6.5.4. Exploratory analysis***

The QTc prolongation pre- and post-PEP among participants who report diarrhea as an AE will be examined as an exploratory objective. Any surplus remaining serum may be used for exploratory analyses of leprosy related biomarkers at the LUMC. These analyses are not covered in the current SAP and are not a part of the main clinical trial.
